2.1.2 Secondary Study Objectives

Secondary objectives and associated endpoints are presented in Table 2.2.

Table 2.2 Secondary Objectives and Associated Endpoints

Type	Objective	Endpoint(s)
Efficacy	To evaluate the effect of MEDI6012 on systolic function of the LV compared to placebo.	EF measured by cine MRI at 10-12 weeks post-MI compared to placebo.
Efficacy	To evaluate the effect of MEDI6012 on non-calcified coronary plaque regression/progression from baseline to 10-12 weeks compared with placebo.	Change in NCPV in the coronary arteries from index CTA to 10-12 weeks post-MI compared with placebo.
Efficacy	To evaluate the effect of MEDI6012 on remodeling of the left ventricle measured by myocardial mass and volumes.	Myocardial mass and LV volumes at end-systole and end-diastole.
Safety	To evaluate the safety and tolerability of MEDI6012.	Incidence of TEAEs and TESAEs.

Table 2.2 Secondary Objectives and Associated Endpoints

Type	Objective	Endpoint(s)
PK, and Immunogenicity	To describe the PK and immunogenicity of MEDI6012.	LCAT mass and presence of ADAs.

ADAs = anti-drug antibodies; CTA = computed tomography angiography; EF = ejection fraction; LCAT = lecithin-cholesterol acyltransferase; LV = left ventricular; MI = myocardial infarction; MRI = magnetic resonance imaging; NCPV = non-calcified plaque volume; PK = pharmacokinetic(s); TEAE = treatment-emergent adverse event; TESAE = treatment-emergent serious adverse event.

2.1.3 Exploratory Study Objectives

Exploratory objectives and associated endpoints are presented in Table 2.3.

Table 2.3 Exploratory Objectives and Associated Endpoints

Type	Objective	Endpoint(s)
Biomarker	To determine whether MEDI6012 [REDACTED]	[REDACTED]
Biomarker	To evaluate the effect of MEDI6012 [REDACTED]	[REDACTED]
Safety	To evaluate the effect of MEDI6012 [REDACTED]	[REDACTED]
Efficacy	To evaluate the effect of MEDI6012 [REDACTED]	[REDACTED]
Efficacy	To evaluate the effect of MEDI6012 on [REDACTED] in serum creatinine of ≥ 0.5 mg/dL (≥ 44 μ mol/L)	[REDACTED]

CTA = computed tomography angiography; CV = cardiovascular; MI = myocardial infarction; pPCI = primary percutaneous coronary intervention; TFG = TIMI flow grade; TIMI = thrombolysis in myocardial infarction.

[figure not shown]
2.2 Study Design

This is a Phase 2b, randomized, placebo controlled- study to evaluate the efficacy, safety, pharmacokinetics/pharmacodynamics (PK/PD), and immunogenicity of repeat doses of MEDI6012 in adult subjects with acute ST segment elevation myocardial infarction (STEMI). The subject and MedImmune staff will be blinded; study sites will be trained to keep the investigator blinded. However, due to the acute nature of the study, members of the study team, and possibly the investigator, may be unblinded.

At least 540 subjects are planned to be randomized across approximately 43 study sites in approximately 10 countries to evaluate a [REDACTED] and a [REDACTED] of MEDI6012.

Due to the acute nature of this study, there will be a very short screening period. The study will enroll subjects presenting with acute STEMI within 6 hours of symptom onset who are planned for emergent primary percutaneous coronary intervention (pPCI). After obtaining verbal or written informed consent (as per local regulations), subjects will be assessed for eligibility, and if considered eligible, will be randomized in a 1:1 ratio into either Cohort A ([REDACTED]) or Cohort B ([REDACTED]). Within each cohort/dose regimen, subjects will be randomized in a 2:1 ratio to receive MEDI6012 or placebo prior to pPCI. In the event a dose regimen (Cohort A or Cohort B) is dropped at the interim analysis, subjects will be randomized in a 1:1 ratio to receive MEDI6012 or placebo for the remaining dose regimen.

[figure not shown]
Figure 2.1 Overall Study Schema

[figure not shown]
CMR = cardiovascular magnetic resonance (imaging); CTA = computed tomography angiography; D = study day; N = number of subjects; pPCI = primary percutaneous coronary intervention; STEMI = ST elevation myocardial infarction.

The study flow diagrams for Cohort A and Cohort B are presented in Figure 2.2 and Figure 2.3, respectively.

Figure 2.2 Study Flow Diagram for Cohort A: [REDACTED]

CCU = cardiac care unit; CMR = cardiovascular magnetic resonance (imaging); D = day; ED = emergency department; PCI = percutaneous coronary intervention; STEMI = ST elevation myocardial infarction.

Figure 2.3**Study Flow Diagram for Cohort B: [REDACTED]**

CCU = cardiac care unit; CMR = cardiovascular magnetic resonance (imaging); CTA = computed tomography angiography; D = day; ED = emergency department; PCI = percutaneous coronary intervention; STEMI = ST elevation myocardial infarction.

2.3 Treatment Assignment and Blinding

An IXRS will be used for randomization to a treatment regimen. A subject will be considered randomized into the study when the investigator notifies the IXRS that the subject meets eligibility criteria. Randomization will be stratified by infarct location. Subjects will be randomized in a 1:1 ratio to one of 2 cohorts, Cohort A ([REDACTED]) and Cohort B ([REDACTED]). Within each dose regimen, subjects will be randomized in a 2:1 ratio to receive MEDI6012 or placebo, see Figure 2.1.

[figure not shown]
In the event that a dose regimen is dropped at the interim analysis, subjects will be randomized in a 1:1 ratio to receive MEDI6012 or placebo for the remaining dose regimen.

The randomization will be stratified by infarct location, ensuring a similar distribution of anterior vs non-anterior infarcts between the active and placebo groups. In addition, the distribution of subjects with anterior versus non-anterior MIs will be monitored over the course of the study. The goal is that > 50% of the final randomized population will be anterior MI. Therefore, the number with non-anterior MI will be monitored via the IXRS and capped by the study team.

This is a blinded study in which MEDI6012 and placebo are nearly identical in appearance. The subject/legal representative and the Sponsor will not be aware of the treatment received

(ICH E9). The unblinded individual preparing the first dose of investigational product for administration in the catheterization laboratory will be aware of the treatment received. The unblinded administrator will be trained to not reveal treatment assignment to the investigator or other clinical and study staff. The site will be asked to take reasonable steps to maintain the blind. Subsequent doses after Dose 1 will be prepared by an unblinded pharmacist. Sites are encouraged to take all reasonable steps to keep site staff involved in follow up assessments after Day 1 blinded to randomization group.

2.4 Sample Size

3 STATISTICAL METHODS

3.1 General Considerations

An initial database lock for the purpose of clinical study analysis and reporting will be performed when the last randomized subject completes the Day 70 to 84 visit or is discontinued prior to that visit; if no subjects are ongoing in the Extended Follow-up period, then this database lock will be considered the final database lock for the study.

If subjects are ongoing in the Extended Follow-up period, a second database lock will occur after all subjects who entered the Extended Follow-up period have completed their Week 25,

39, or 52 visits as needed or are discontinued prior to these visits, and this will be considered the final database lock. If the last Extended Follow-up visit occurs before the last Day 70 to 84 visit on the study, the second database lock will not be needed.

The study will be unblinded to the sponsor at the time of initial database lock. The site, subjects, and local CRO personnel will remain blinded to treatment assignment until the final database lock is declared.

Safety data will be generated for the Extended Follow-up period and summarized as an addendum to the clinical study report.

Data will be provided in listings sorted by treatment group and subject number. Tabular summaries will be presented by treatment group with placebo group combined when appropriate. Categorical data will be summarized by the number and percentage of subjects in each category. Continuous variables will be summarized by descriptive statistics. Baseline values will be defined as the last valid assessment prior to the first administration of investigational product on Day 1 unless data are missing, in which case, baseline will be defined as the last value prior to dosing. All statistical tests will be one-sided (based on protocol amendment) at an alpha = 0.05 significance level unless stated otherwise.

Confidence intervals will be one-sided (based on protocol amendment) and nominal p-values will be reported when appropriate.

Data analyses will be conducted using the SAS® System Version 9.3 or higher (SAS Institute Inc., Cary, NC) unless otherwise specified.

3.2 Analysis Populations

The analysis populations are defined in Table 3.1.

Table 3.1 Analysis Populations

Population	Description
ITT Population	The ITT Population consists of subjects who are randomized, and will be analyzed according to their randomized treatment group.
As-treated Population	The As-treated Population consists of randomized subjects who receive any study investigational product. Subjects who receive only placebo doses will be analyzed with the placebo group; conversely, subjects who receive any dose of MEDI6012 will be analyzed with the MEDI6012 group.
Primary Efficacy Analysis Population	Randomized subjects who receive at least [REDACTED] doses of investigational product with TFG 0 or 1 on initial angiography. Subjects who receive all placebo doses will be analyzed with the placebo group; conversely, subjects who receive [REDACTED] doses of MEDI6012 will be analyzed with the MEDI6012 group.

Table 3.1 **Analysis Populations**

Population	Description
Efficacy Analysis Population –TIMI 2-3	Randomized subjects who receive at [REDACTED] doses of investigational product with TFG 2 or 3 on initial angiography. Subjects who receive all placebo doses will be analyzed with the placebo group; conversely, subjects who receive [REDACTED] of MEDI6012 will be analyzed with the MEDI6012 group.
Efficacy Analysis Population TIMI –0-3	Randomized subjects who receive at [REDACTED] of investigational product with TFG 0 to 3 on initial angiography. Subjects who receive all placebo doses will be analyzed with the placebo group; conversely, subjects who receive [REDACTED] doses of MEDI6012 will be analyzed with the MEDI6012 group.
CTA Analysis Population	Randomized subjects in the [REDACTED] regimen who receive a full treatment course of investigation product. The subjects who receive [REDACTED] placebo doses will be analyzed with the placebo group; conversely, subjects who receive [REDACTED] dose of MEDI6012 will be analyzed with the MEDI6012 group.
Immunogenicity Population	All subjects in the as-treated population who have at least one serum sample for immunogenicity testing.
PK Population	All subjects in the as-treated population who have at least one detectable serum concentration measurement for LCAT mass.

CTA = computed tomography angiography; ITT = Intent-to-treat; LCAT = lecithin-cholesterol acyltransferase; PK = pharmacokinetic; TFG = TIMI flow grade; TIMI = Thrombolysis in Myocardial Infarction.

3.3 Study Subjects

3.3.1 Subject Disposition and Completion Status

A summary of subject eligibility and randomization as well as treatment group received (including summary of subjects randomized but not treated) will be provided. In addition, disposition of subjects throughout the study with respect to completion of treatment and follow-up will be provided.

3.3.2 Demographics and Baseline Characteristics

Demographic information related to sex, age, race, ethnicity, weight, height, and body mass index will be presented by treatment group and for all subjects combined. A summary of baseline disease characteristics may include, but not be limited to medical history and acute cardiovascular disease history.

3.3.3 Study Drug Exposure

The number of subjects for the exposure to investigational product will be summarized descriptively by the total number of dose received.

The entire dose administered (ie, Yes vs No), the reason(s) why the subject was not administered entire dose and the reason(s) why the subject did not receive any investigational product (ie, adverse events [AEs] vs other) will be provided in the listing.

3.3.4 Concomitant Medications

Concomitant medications will be coded using the latest available version of the World Health Organization Drug Dictionary and summarized by preferred term with frequency and percentage by treatment group. In addition, concomitant medications will be summarized by Anatomical Therapeutic Chemical Classification System.

3.4 Efficacy Analyses

3.4.1 Primary Efficacy Endpoint(s) and Analyses

3.4.1.1 Primary Efficacy Endpoint(s)

The primary efficacy endpoint is the infarct size, expressed as a percentage of LV mass measured on delayed-enhanced CMR imaging, in 10–12 weeks post- MI.

3.4.1.2 Handling of Dropouts and Missing Data

Missing data will not be imputed.

3.4.1.3 Primary Efficacy Analysis

The primary efficacy endpoint is the infarct size in 10-12 weeks post MI. The endpoint will be log-transformed due to its skewed distribution and be analyzed by means of 2-sample t-test. The treatment effect is estimated by the geometric mean ratio of MEDI6012 to placebo as well as its 95% CI. Infarct size records with zero value, will be imputed by half of the minimum of the non-zero records prior to the log transformation.

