3.2.2 Rationale for Study Population

The current study is intended to examine the cardioprotective and atherosclerotic effects of MEDI6012 in subjects with acute STEMI. In comparison to acute non-STEMI, patients with acute STEMI, particularly acute anterior STEMI, experience larger myocardial infarcts that result in greater reductions in EF. Since it is likely that subjects with larger infarcts will be more likely to benefit from MEDI6012, the study population is planned to have > 50% of subjects with acute anterior STEMI and > 60% with pre-PCI Thrombolysis in Myocardial Infarction (TIMI) flow grade (TFG) 0-1. However, this study will evaluate the effect of MEDI6012 in non-anterior STEMI and those with pre-PCI TFG 2-3 to fully characterize the potential efficacy of MEDI6012.

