Study participation begins on study Day 1 (ie, a subject is “enrolled”) once the first consent, whether written or verbal is obtained. Following first consent, evaluations to assess study eligibility (inclusion/exclusion criteria) will be performed. A SID (subject identification) number will be used to identify the subject. Dose 1, as assigned following randomization by a central system (eg, an interaction response system [IXRS], which includes interactive voice response system and interactive web response system) may be given once the pre-screening procedures have been completed.

A master log of all consented subjects will be maintained at the site and will document all screening failures (ie, subjects who are consented but do not meet study eligibility criteria and/or are not randomized), including the reason(s) for screening failure.

Subjects who fail to meet the inclusion/exclusion criteria (ie, screening failures) should not be randomized (if applicable) or receive investigational product.

Randomization will be stratified by infarct location, ensuring balanced randomization to active treatment vs placebo within the anterior group and the non-anterior MI groups. In

addition, the distribution of subjects with anterior vs non-anterior MIs will be monitored over the course of the study. The goal is that >50% of the final randomized population will be anterior MI. Therefore, the number with non-anterior MI will be monitored via the IXRS and capped by the study team.

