4.8.3 Efficacy

4.8.3.1 Primary Efficacy Analysis

The primary objective of this study is to evaluate the effect of MEDI6012 on the reduction of infarct size compared with placebo. The primary efficacy endpoint is infarct size as a percentage of LV mass measured on delayed-enhanced CMR imaging 10-12 weeks post- MI.

The primary efficacy endpoint of infarct size will be analyzed using t-test with log-transformation of the data based on the primary efficacy analysis population.

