4.8.3.3 Secondary Efficacy Analyses

Secondary efficacy endpoints include EF measured by cine MRI at 10-12 weeks post-MI, Change in NCPV in the coronary arteries from index CTA to 10-12 weeks post-MI, and Myocardial mass and left ventricular volumes at end-systole and end-diastole.

EF, myocardial mass, and left ventricular volumes will be analyzed similarly to infarct size without the log-transformation of the data.

Change from index CTA in NCPV will be analyzed using t-test based on CTA analysis population.

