3.4.2.3 Secondary Efficacy Analyses

EF, myocardial mass, and left ventricular volumes will be analyzed using t-test, if appropriate, based on the Primary Efficacy Analysis Population, the Efficacy Analysis Population – TIMI 2-3; Efficacy Analysis Population – TIMI 0-3; as treated, and the ITT Population.

Change from index CTA in NCPV will be analyzed using t-test, if appropriate, based on CTA Analysis, As-treated, and ITT Populations.

Parameters will first be evaluated for normality which will be evaluated using Q-Q plots.

If the distribution appears to be normal, the endpoint will be analyzed by a 2-sample t-test. The treatment effect is estimated by difference in means of MEDI6012 to placebo as well as its 95% CI.

If the distribution appears to be log-normal, the endpoint will be log-transformed due to its skewed distribution and be analyzed by a 2-sample t-test. The treatment effect is estimated by the geometric mean ratio of MEDI6012 to placebo as well as its 95% CI.

Non-parametric (distribution-free) methods will be applied to the endpoint data if applicable.

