4 INTERIM ANALYSIS

Two interim analyses are planned. The objectives of the first interim analysis will be to assess futility and potentially to drop a dose regimen. The analysis, which will be conducted after 30% of the Primary Efficacy Analysis Population (assumed 40% rate of exclusion from the primary efficacy analysis population is expected due to TFG 2 or 3 flow in the infarct-related artery on initial angiography and other reasons for subsequent exclusion or drop-out) based on the original sample size ($N = 74$) is enrolled, will require that $> 50\%$ of subjects ($N > 37$) have acute anterior STEMI and have completed their final study visit. The first interim analysis will be conducted through the Independent Data Monitoring Committee (IDMC). The second interim analysis is planned to accelerate decision on future development options for MEDI6012 and will be performed once 60% of the Primary Efficacy Analysis Population (assumed 50% rate of exclusion from the primary efficacy analysis population is expected due to TFG 2 or 3 flow in the infarct-related artery on initial angiography and other reasons for subsequent exclusion or drop-out) based on the revised sample size ($N = 162$) is enrolled and will require that $> 50\%$ of subjects ($N > 81$) have acute anterior STEMI and have completed their final study visit. Details of the second interim analyses will be specified in the unblinding plan. The sponsor and Principal Investigator will monitor the statistical assumptions in a blinded fashion and schedule the interim analyses accordingly.

The assessment of futility will be based on predictive power, which is conditional power averaged over the distribution of the observed treatment effect at the time of interim analysis. The futility analysis will include all available data at the time of the interim data cut.

The predictive power based on the empirical trend observed at the interim analysis will be calculated by

$$\text{predictive power } pp = \Phi\left(\frac{z_\tau - z_{1-\alpha/2}\sqrt{\tau}}{\sqrt{1-\tau}}\right)$$

τ is the information fraction at the interim analysis, z_τ is the observed value of the test statistic at the interim, α is the two-sided significance level at the final analysis based on the original protocol, and Φ is the standardized normal density function.

Each MEDI6012 dose regimen will be compared to the combined placebo group (pooled over dose regimens).

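### The primary t-test omits infarct location, the randomisation stratum: it is valid, but mildly conservative and less precise than a location-adjusted model

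*SAP*

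**What the plan says.** SAP section 2.3 describes the allocation: "The randomization will be stratified by infarct location, ensuring a similar distribution of anterior vs non-anterior infarcts between the active and placebo groups". Protocol section 4.1.5 agrees: "Randomization will be stratified by infarct location, ensuring balanced randomization to active treatment vs placebo". Both documents also aim for more than half of those randomised to have anterior infarcts and allow non-anterior enrolment to be capped.

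Protocol section 3.2.2 gives the reason location matters. STEMI patients, "particularly acute anterior STEMI, experience larger myocardial infarcts", and these larger infarcts go with greater falls in EF.

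The primary test does not use location. SAP section 3.4.1.3: "The endpoint will be log-transformed due to its skewed distribution and be analyzed by means of 2-sample t-test". Protocol section 4.8.3.1: "The primary efficacy endpoint of infarct size will be analyzed using t-test with log-transformation of the data based on the primary efficacy analysis population". The other CMR endpoints follow the same pattern. Protocol section 4.8.3.3: "EF, myocardial mass, and left ventricular volumes will be analyzed similarly to infarct size without the log-transformation of the data". SAP section 3.4.2.3: "EF, myocardial mass, and left ventricular volumes will be analyzed using t-test, if appropriate".

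In the visible text, location enters the analysis only as a subgroup factor (SAP sections 3.4.1.5 and 3.4.2.4).

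**The concern.** When a prognostic factor is balanced by stratified randomisation, the true variance of the treatment difference falls. A two-sample t-test still estimates its standard error from the total variance, including the between-stratum part. The test is then conservative and the confidence limit wider than it need be. A model containing the stratum removes that variance.

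Stratification does not make adjustment redundant here, because the primary population is a subset defined after randomisation. SAP section 4 records an "assumed 50% rate of exclusion from the primary efficacy analysis population is expected due to TFG 2 or 3 flow" and other reasons. Stratified balance is therefore only partly kept among the subjects analysed. An unadjusted test does nothing about the location imbalance that remains.

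**Working it through.** **Plan figures that can be reproduced.** Protocol section 4.8.2 gives 90 evaluable per arm for 80% power at one-sided 0.05, and 180 randomised per arm. With 50% exclusion, 90/(1 − 0.5) = 180, and three comparison groups give 540. The second interim is 0.6 × 0.5 × 540 = 162, as stated. The 80% itself cannot be reproduced, because the effect and the coefficient of variation (CV) are redacted.

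**Log-scale SD, low end (from SAP section 4).** A predictive power of 50% is tied to an 18% reduction at information fraction 0.30.
- z = 1.96 × √0.30 = 1.0735
- SE = −ln(0.82)/1.0735 = 0.1849
- With 74/3 = 24.67 per arm, SD = 0.1849/√(2/24.67) = 0.649
- Check 1: 20% predictive power needs z = 1.0735 − 0.8416 × √0.70 = 0.369, so the reduction is 1 − exp(−0.369 × 0.1849) = 6.6% (SAP: about 7%).
- Check 2: the original 414/3 × 0.6 = 83 per arm gives a detectable effect of 1 − exp(−1.96 × 0.649 × √(2/83)) = 17.9% (SAP: 18%).

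**Log-scale SD, high end (assumption).** Suppose the target effect and 80% power were kept when the plan moved from 83 per arm at two-sided 0.05 to 90 per arm at one-sided 0.05.
- Target log effect = (1.96 + 0.8416) × 0.649 × √(2/83) = 0.282
- SD = 0.282/[(1.645 + 0.8416) × √(2/90)] = 0.76; 0.77 is used below.

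**Variance explained by location.** With half the subjects anterior (assumption), R² = 0.25 × ln(ratio)²/SD², where ratio is the anterior/non-anterior geometric mean ratio (assumed; not in the documents).

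**Simulation.** 60,000 runs per case; 180 per arm with exactly 90 anterior; 90 per arm retained at random; one-sided 5%; effect set to give the t-test 80% power at the total SD. Each cell shows SD 0.65 / SD 0.77.

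| Ratio | R² (%) | Type I error, t-test (%) | Type I error, adjusted (%) | Power, t-test (%) | Power, adjusted (%) | Gain (points) |
|---|---|---|---|---|---|---|
| 1.0 | 0 | nominal | nominal | 79.6 / 79.7 | 79.6 / 79.6 | 0.0 / −0.1 |
| 1.25 | 2.9 / 2.1 | 4.8 / 5.0 | 4.9 / 5.1 | 80.0 / 79.9 | 80.7 / 80.5 | 0.7 / 0.6 |
| 1.5 | 9.7 / 6.9 | 4.8 / 4.8 | 5.1 / 5.1 | 80.3 / 80.0 | 83.0 / 82.1 | 2.7 / 2.1 |
| 2.0 | 28.4 / 20.3 | 3.8 / 4.2 | 4.9 / 5.0 | 81.7 / 80.9 | 90.1 / 86.7 | 8.4 / 5.8 |

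Monte Carlo error on a 5% rate is √(0.05 × 0.95/60,000), about 0.1 point. With 60% anterior, power is within about 1 point of these figures.

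**Analytic checks.**
- Keeping a random half leaves about half of the between-stratum variance in the difference. The t-test's size is then about Φ(−1.645/√(1 − R²/2)): 4.9% at ratio 1.25, 4.6–4.7% at 1.5, and 3.8–4.1% at 2.0.
- The standard error shrinks by 1 − √(1 − R²): 1.1–1.5%, 3.5–5.0% and 10.7–15.4%.
- Put as sample size, the adjusted model needs about 90 × (1 − R²) per arm: 86, 81 and 72 for R² of 5%, 10% and 20%.

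**Residual imbalance.** Under the same random retention, the between-arm difference in anterior share has SD √(2 × 0.25/90 × 90/179) = 0.053. A difference above 10 percentage points therefore occurs in about 6% of trials.

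**The case against.** The strongest reply is that nothing here is an error. The t-test holds its level, keeps about 80% power in every case above, and matches a sample size built on total variability. Location is already stratified, monitored and examined by subgroup. This is a Phase 2b trial reporting nominal p-values. All of that stands, and it is why this is an efficiency point only. Subgroup results, however, do not adjust the overall estimate.

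The size rests on assumptions. The protocol says anterior infarcts are larger but gives no ratio. The SD of 0.65 comes from an interim illustration built on the original sample size, and Amendment 5 changed the sample size because of the CV observed in blinded data. The 0.77 column is arguably closer to the current plan: gains of 0.6, 2.1 and 5.8 points. That is a fair reason to discount the top of the range, but the direction is unchanged.

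The protocol links location to infarct size and EF, not expressly to LV mass or volumes. Using the same covariate there is for consistency; no gain has been calculated for any secondary endpoint.

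SAP section 3.4.3 has no visible text and could contain a supportive adjusted analysis. It would not alter the primary test named in section 3.4.1.3.

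Finally, the futility rule in SAP section 4 uses the interim test statistic, so changing the final test needs a matching sentence there. That is a small edit.

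**Conclusion.** The point holds. The primary analysis omits a stratification factor that the protocol itself treats as prognostic. The consequence is mild conservatism and lost precision, not a false-positive problem. The gain from adjusting is under 1 point of power up to a ratio of 1.25, 2 to 3 points at 1.5 and 6 to 8 points at 2.0. The t-test's type I error falls to about 4% at a ratio of 2.0. These figures assume 50% anterior, random retention of half of each arm, equal log-normal variances, and SD 0.65 to 0.77.

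One condition applies to the word valid. Protocol section 4.2.1.1 sends all later subjects to Cohort B at 1:1, so the Cohort A comparison with pooled placebo includes placebo subjects enrolled after Cohort A closed. If the anterior share drifted, location would be imbalanced in that comparison. For illustration, assume 20% enrolled after the change, anterior share rising from 50% to 70%, ratio 1.5 and SD 0.776. The imbalance is then 0.20 × 0.1/(0.8/3 + 0.1) = 0.055, a shift of 0.055 × ln 1.5/(0.776 × √(2/90)) = 0.19 standard errors, and the one-sided error is about 7%. Without drift it is about 4.7%. Cohort B against placebo is unaffected. Location adjustment would remove this imbalance too.

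**What to change.** In SAP section 3.4.1.3 and protocol section 4.8.3.1, make the primary analysis a linear model on log infarct size with treatment and infarct location (anterior versus non-anterior) as recorded in the IXRS at randomisation. Report the adjusted geometric mean ratio with its confidence limit, and keep the unadjusted t-test as a sensitivity analysis. Use the same covariate for EF, LV mass and LV volumes in SAP section 3.4.2.3 and protocol section 4.8.3.3. Add a sentence to SAP section 4 saying which test statistic the futility calculation refers to. Settle this before the initial database lock, when the sponsor is unblinded.

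The cost is one degree of freedom and matching text edits. The covariate is already held, so no new data are needed.
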